9. DATA COLLECTION

9.1. CONSTRUCTS AND MEASURES

Clearly articulate the constructs of interest, measures to evaluate those constructs, and specific data collection instruments. Provide any information on the reliability and validity of the data collection instruments. For standardized instruments, you may provide the citation for the instrument.

Construct	Measure	Instrument	Reliability and Validity
Parenting Behavior	1 item: hours spent with children in last 30 days (interval); 1 item: frequency reaching out to children (categories, 5-point scale); 7 items: frequency engaging in key behaviors (categories, 5-point scale)	nFORM Community-Based Fathers Survey (A2b, A2c, A5b: b-d, f-i)	nFORM
Parenting Attitudes	7 items: frequency of key attitudes (categories, 5-point scale)	nFORM Community-Based Fathers Survey (A3: a-g)	nFORM

Co-Parenting Behavior	11 items: frequency of agreement with key co-parenting behaviors (interval, 5-point scale)	nFORM Community-Based Fathers Survey (A13: a-k)	nFORM
Employment Attitudes	2 items: level of agreement with attitudes related to acquiring a job and providing for a family .	OLLE (Online Local Evaluation) Survey	Jurkiewicz, T. & Friedman, L. (2020). Impact Evaluation of The TYRO Champion Dads Project in Dallas, Texas: Final Impact Evaluation Report for Anthem Strong Families. Midwest Evaluation and Research.

9.2. CONSENT

Describe how and when program applicants will be informed of the study and will have the option of agreeing (i.e., consenting to) or declining to participate in the study.

Because the planned evaluation involves human subjects, GCT understands program implementation requires both IRB approval and participant informed consent. MER has an established relationship with Solutions IRB, having secured more than 20 IRB approvals and renewals for evaluations it has conducted during the past five years. IRB clearance will be submitted for approval and obtained during the planning period.

To secure informed consent, participants will attend an orientation / enrollment session (in person or virtual) where the Data Manager will describe the evaluation process and the risks and benefits of the project. An IRB-approved Q&A video can be played during orientation to provide more information about the evaluation study as needed. Those people that wish to participate in the evaluation will complete an informed consent process and sign an informed consent document / form. All participants will receive a copy of the consent form with contact information for evaluation staff and how to contact the IRB with any questions or to withdraw from the study. Informed consent will take place prior to the collection of evaluation data.

9.3. METHODS OF DATA COLLECTION

If the evaluation will collect multiple waves of data, describe the timing of these waves below. When describing follow-up periods, specify whether the follow-up period will be post-baseline, post-random assignment, or post-program completion.

Wave of Data Collection	Timing of Data Collection
-------------------------	---------------------------

(e.g., baseline, short-term follow-up, long-term follow-up)	
Baseline	Collected immediately following informed consent and study enrollment – during orientation session or first workshop
Post-test	Collected after the completion of the primary services programming – during the last workshop session or exit session – approximately 7 to 13 weeks after enrollment depending on delivery schedule
1 year follow-up (post-baseline)	Collected approximately one year after study enrollment/baseline

For each measure, describe how data will be collected detailing which data collection measures will be collected by which persons, and at what point in the programming or at what follow-up point.

Survey	Timing of Data Collection (baseline, wave of data collection)	Method of Data Collection	Who Is Responsible for Data Collection?	Will Methods or Collection Procedures Differ by Study Group?	Will data access require data sharing agreement?
On-Line Local Evaluation (OLLE) and nFORM Baseline Surveys	Baseline	Participant self-enters survey using online data collection platform	Data Manager will proctor data collection and assist participants as necessary	No	N/A
OLLE and nFORM Post-Test Surveys	Post-Test (approx. 7 to 13 weeks after enrollment)	Participant self-enters survey using online data collection platform	Data Manager will proctor data collection and assist participants as necessary	No	N/A

OLLE 1 Year Follow-up Survey	1 year after enrollment / baseline	Participant self-enters survey using online data collection platform and link – or – Phone interview data collection with evaluation staff	MER Research Staff/ participant tracking team	No	N/A
------------------------------	------------------------------------	--	---	----	-----

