3. EVALUATION ENROLLMENT

Please provide the expected start and end dates for program and evaluation enrollment using the tables below.

IMPLEMENTATION EVALUATION		
Please leave blank if not conducting an implementation study.		
	Program Enrollment	Study Enrollment
Start Date	05/01/2021	05/01/2021
End Date	07/15/2025	07/15/2025

Definition	Program implementation metrics using data from nFORM (e.g., workshop hours received, enrollment, retention, etc.), site visit findings, CQI process findings	Same as program enrollment
-------------------	--	----------------------------

DESCRIPTIVE EVALUATION		
Please leave blank if not conducting a descriptive outcome evaluation.		
	Program Enrollment	Study Enrollment
Start Date	05/01/2021	05/01/2021
End Date	07/15/2025	06/15/2024
Definition	Eligible low-income fathers and father figures in the Central Texas area, 18 years of age or older, with children under the age of 24	All participants who consent to be part of the evaluation study

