4. EVALUATION TIMELINE

Please include a timeline for key activities of the evaluation below.

Evaluation Activity	Start Date	End Date
Additional evaluation staff hiring and onboarding	1/15/2021	2/15/2021
Evaluation staff training	1/22/2021	2/20/2021
Evaluation kickoff meeting and orientation with all program staff	2/10/2021	2/10/2021
IRB training and certification by all program and evaluation staff	10/1/2020	3/09/2021
Development and submission of descriptive evaluation plan document	7/25/2022	8/25/2022
Evaluation Tools Development	10/1/2020	10/15/2021
IRB Approval	3/22/2021	3/29/2021 – initial approval

		4/6/2022 – amendment approval
CQI Team Formed and Meeting bi-weekly	5/20/2021	7/1/2025
Training for CQI Team	3/15/2021	3/28/2021 Ongoing as needed
Training for all Program Staff on Research Methods and process	3/15/2021	4/12/2021 Ongoing as needed
Implementation Evaluation Data Collection	4/15/2021	6/15/2025
Evaluation Program Staff Training	3/15/2021	Ongoing as needed
Preliminary Implementation Report Submitted	6/31/2022	6/31/2022
Descriptive Study Data Collection		
- Randomization	-	-
- Baseline	4/15/2021	3/31/2024
- Post Test	7/8/2021	5/31/2024
- Follow-up	4/15/2022	6/15/2025
Final Implementation Report Submitted	9/1/2025	9/29/2025
Final Report Submitted	9/1/2025	9/29/2025

EVALUATION PLAN

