----------------------	------------------------	--	---	---------	---

Handling missing data

Outcomes

When creating the composite measures for co-parenting and parenting relationships, we will create a composite score by taking the average of multiple individual items. For these measures, our current plan is to use 20% as a threshold for allowable missing items, based on guidance from evaluation technical assistance resources. This plan is contingent on the final distribution of missing data in our data set. We will not be imputing truly missing values for outcomes. To create a construct score, the average will divide by the number of non-missing values in the construct.

Participants who have not seen their child within the past month will have their parenting behavior responses set to “Never” (1) and will be included in the analytic sample for that outcome.

For outcomes that use single survey items, participants who do not respond to the item on either the pre-survey or follow-up survey will be excluded from the analytic sample for that outcome.

Missing data for the implementation outcomes could happen as a result of programmatic data entry issues. For the sake of this evaluation, we assume that any primary or support services received by a participant are being accurately logged into nFORM, so a lack of documented attendance, service contacts, referrals, etc. is indicative of lack of services (i.e., a participant not receiving the program components as intended).

Assessing non-response bias

We will conduct response rate analysis for each primary outcome of interest to assess non-response bias and adjust for threats to internal validity. Using data from the Applicant

Characteristics Survey, we will look at demographics (race, ethnicity, age, education level) and primary reason for joining the program among participants who fall into each of the following categories: 1) non-respondents who answered no surveys after the ACS, 2) respondents who completed the pre-survey only, 3) respondents who completed the follow-up survey only, and 4) respondents who completed both a pre- and follow-up survey (complete case).

Analytic approach

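### Baseline and post-test collection close too early for the stated enrollment and timing rules, and implementation data close before enrollment ends with no dosage rule for late entrants

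*Protocol*

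**What the plan says.** **Enrollment dates (Protocol section 3).** Descriptive-study enrollment opens 05/01/2021 and closes 06/15/2024; the table row reads "End Date 07/15/2025 06/15/2024", the second date being the study's. The enrolled group is defined as "All participants who consent to be part of the evaluation study". For the implementation evaluation, program and study enrollment both run from 05/01/2021 to 07/15/2025.

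**Collection dates (Protocol section 4).** Under "Descriptive Study Data Collection", baseline runs to 3/31/2024, post-test to 5/31/2024 and follow-up to 6/15/2025. The row "Implementation Evaluation Data Collection" ends 6/15/2025.

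**Timing rules (Protocol section 9.3).** Baseline is "Collected immediately following informed consent and study enrollment", at orientation or the first workshop. Post-test comes at the end of primary services, "approximately 7 to 13 weeks after enrollment depending on delivery schedule". Follow-up is about one year after enrollment.

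**Analysis rules (SAP section 1).** Every outcome is a change from a pre-program score. Only parenting attitudes (R2) uses the post-test; the other outcomes use the one-year follow-up. For implementation, services are assumed to be logged accurately, "so a lack of documented attendance, service contacts, referrals, etc. is indicative of lack of services". Fidelity is the percentage of enrolled men with any receipt of each of four components, set against 100%. Dosage is the mean percentage of target workshops attended, set against 90%, plus attendance categories (initial, halfway, 90%, 100%).

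**The concern.** If baseline is taken at enrollment, the two must close on the same day, and post-test must stay open at least one full delivery schedule beyond that. Neither holds. A man without a baseline has no change score for R1 to R4, even if he is later reached at one year. A man whose post-test falls due after the window closes drops out of R2, which the Protocol labels confirmatory. That second loss depends on delivery schedule: it removes men on longer schedules and keeps those on shorter ones.

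In the implementation study, men who enter near or after the data close cannot have a full attendance record. With no documented attendance read as no service, and no rule for incomplete observation, an administrative cut-off would be reported as a delivery shortfall.

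**Working it through.** The documents give no accrual curve, so shares assume even enrollment over time. Day counts are end date minus start date.

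**Check of the plan's own dates.** Follow-up: 06/15/2024 + 1 year = 06/15/2025, exactly the stated close. So follow-up was set for enrollment to 06/15/2024. Baseline and post-test do not reproduce in this way.

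**Baseline.** Required close = enrollment close + 0 days = 06/15/2024. Stated close = 3/31/2024. Gap = 76 days. Enrollment period 05/01/2021 to 06/15/2024 = 1141 days. Share = 76/1141 = 6.7%.

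**Post-test.** From last baseline to post-test close: 3/31/2024 to 5/31/2024 = 61 days = 8.7 weeks. Any schedule longer than that cannot be completed by men enrolled at the end of the baseline window. Last enrollment date that allows a post-test = 5/31/2024 minus the schedule length:

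| Schedule | Last enrollment date for a post-test | Post-test due if enrolled 3/31/2024 | Post-test due if enrolled 06/15/2024 |
|---|---|---|---|
| 7 weeks | 4/12/2024 | 5/19/2024 | 8/3/2024 |
| 13 weeks | 3/1/2024 | 6/30/2024 | 9/14/2024 |

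**Loss under each reading of the enrollment close.**

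- *Close is 06/15/2024.* No baseline: 76/1141 = 6.7%, affecting R1 to R4. No post-test: 64/1141 = 5.6% (7 weeks) to 106/1141 = 9.3% (13 weeks). R2 needs both surveys, so its loss is 6.7% on a 7-week schedule, where the missing baseline binds, and 9.3% on a 13-week schedule.
- *Close is 3/31/2024.* Enrollment period = 1065 days. No one lacks a baseline. Men on a 13-week schedule enrolled after 3/1/2024 still miss the post-test: 91 − 61 = 30 days, 30/1065 = 2.8%, and only if everyone were on 13 weeks. On a 7-week schedule the loss is zero.

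**Implementation dosage.** Enrollment 05/01/2021 to 07/15/2025 = 1536 days; to the data close of 6/15/2025 = 1506 days; gap = 30 days. Suppose every man attends everything at an even pace over L days. Men enrolled in the last L days before the data close are then recorded at half dosage on average.

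- Enrollment records also stop at 6/15/2025: mean dosage = (1506 − L/2)/1506. For L = 91: 1460.5/1506 = 97.0%. For L = 49: 1481.5/1506 = 98.4%.
- Enrollment records continue to 07/15/2025: mean dosage = (1506 − L/2)/1536. For L = 91: 1460.5/1536 = 95.1%. For L = 49: 1481.5/1536 = 96.5%.

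The share of men who cannot reach the 100% attendance category is 49/1506 = 3.3% to 91/1506 = 6.0% in the first case, and 79/1536 = 5.1% to 121/1536 = 7.9% in the second.

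**Fidelity (any receipt).** If men enrolled after 6/15/2025 stay in the denominator with no service record, the maximum is 1506/1536 = 98.0%. If they leave with their records, that ceiling disappears.

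**The case against.** A reader might infer that all data collection in the descriptive study closes before enrollment does. It does not: the follow-up window fits 06/15/2024 to the day.

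A reader might also take 6.7% and 9.3% as expected losses. They arise only if men are still being enrolled after baseline collection has stopped. Section 9.3 itself implies that anyone enrolled is given a baseline, and if 3/31/2024 is the true enrollment close nobody lacks one. This objection stands, and the figures must stay conditional. The post-test conflict survives it, because 8.7 weeks is shorter than the upper end of the stated range even with enrollment ending on 3/31/2024. The word 'approximately' softens the range but does not absorb a gap of more than four weeks.

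On implementation, the strongest inference would be that late entrants are counted as not served against both benchmarks. The documents do not support that. A man partway through has already received a primary workshop, so he meets that any-receipt measure. On mean dosage he gets partial credit and is under-dosed, not unserved. Enrollment is itself listed among the nFORM metrics in Protocol section 3, so men enrolled after the data close may leave numerator and denominator together. The SAP's rule on undocumented services is written about data entry problems, not truncated observation. Staff may also go on recording after 6/15/2025: the CQI team, which reviews nFORM data, meets until 7/1/2025, and final reports are due in September 2025.

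These points narrow the issue without removing it. Nothing says the evaluation will use records made after the stated close. Men enrolled in the 7 to 13 weeks before it still have truncated attendance, and the SAP gives no other rule for them. Continued nFORM entrance surveys would not rescue R4 either, since its baseline comes from the local OLLE pre-survey.

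**Conclusion.** The dates are inconsistent as written, and no section reconciles them. The consequences are modest and depend on which date is right. In the descriptive study, the loss is 6.7% of enrollees for every outcome (up to 9.3% for R2) if enrollment really runs to 06/15/2024 and the collection closes are followed. It is at most 2.8%, for R2 only and only on schedules longer than 8.7 weeks, if enrollment really ends on 3/31/2024. The mix of schedules is not given, so the actual R2 loss cannot be fixed within these limits.

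In the implementation study, mean dosage and the upper attendance categories are biased slightly downward. Under perfect, even-paced attendance the mean still clears 90%, so the benchmark is reachable. The bias could change the comparison only for a program whose true mean is a little above 90%: if the shortfall scales proportionally, recording 90% would need a true mean of 0.90/0.970 = 92.8% (13 weeks, enrollment records also stopped). The any-receipt measures are affected mainly for men enrolled around or after the data close, and only if they remain in the denominator. All shares rest on even accrual.

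**What to change.** 1. In Protocol sections 3 and 4, use one date for study enrollment close and baseline close. Set post-test close 13 weeks later: 6/30/2024 if 3/31/2024 stands, or 9/14/2024 if 06/15/2024 stands.
2. While correcting the table, reconcile the opening dates too: baseline collection opens 4/15/2021, 16 days before enrollment opens on 05/01/2021.
3. In the SAP, state the implementation data cut-off and whether enrollment records stop on the same day.
4. Compute mean dosage and the attendance categories only in men enrolled at least 13 weeks before that cut-off (6/15/2025 − 91 days = 3/16/2025). List later entrants separately as incomplete follow-up.
5. For the any-receipt fidelity measures, exclude only men enrolled after the data close. Dropping all entrants after 3/16/2025 from these would discard usable data for no gain.

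The cost is a few corrected dates, a longer post-test window, one denominator rule and a slightly smaller dosage denominator.

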1. RESEARCH QUESTIONS

1.1. OVERVIEW OF RESEARCH QUESTIONS

Research questions in this study are framed by a descriptive evaluation design that will be used to measure changes in participant outcomes after participation in the Fatherhood Works Program. Analyses will measure the differences in primary and secondary outcomes from orientation to one year after program enrollment. Primary outcomes refer here to changes in parenting and co-parenting *behaviors*. Secondary outcomes refer here to the *attitudes* that theoretically facilitate and reflect behaviors. Implementation analyses seek to demonstrate whether or not participants are receiving the intended amounts of FWP services.

No	Research Question	Implementation or Outcome?
I1	To what extent is the Nurturing Fathers curriculum offered to and received by program participants?	Implementation
I2	To what extent are additional primary workshops offered to and received by program participants?	Implementation
I3	To what extent did the CQI team carry out the steps in the CQI plan each program year?	Implementation
R1	How did parenting behavior measures change from program enrollment to 1 year after enrollment?	Primary Outcome
R2	How did parenting attitude measures change from program enrollment to immediately following program completion?	Secondary Outcome
R3	How did co-parenting behavior measures change from program enrollment to 1 year after enrollment?	Primary Outcome
R4	How did employment attitude measures change from program enrollment to 1 year after enrollment?	Secondary Outcome

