1.2. OUTCOME RESEARCH QUESTIONS

For each outcome research question listed above, whether a *descriptive* or *impact* design, summarize the inputs (e.g., program components, program supports, implementation features, etc.), target population (e.g., the population for which the effect will be estimated) and the outcomes (e.g., child well-being, father-child engagement, etc.) that will be examined to answer the research question(s). Comparisons for descriptive evaluations may reflect circumstances before the grant, pre-treatment, or pre-determined benchmark from other studies with similar interventions.

Research Question Number Should correspond to the number indicated in Table 1.1 above	Intervention Program component or set of activities that the evaluation will test or examine	Target Population Population for which the effect of the treatment will be estimated	Comparison What the intervention will be compared to (e.g., pre-intervention for descriptive designs)	Outcome Changes that are expected to occur as a result of the intervention	Confirmatory or Exploratory? Confirmatory: those upon which conclusions will be drawn Exploratory: those that may provide additional
--	---	---	--	---	--

					suggestive evidence
R1	Primary program services which include: Nurturing Fathers parenting course, Creating a Safe Home domestic violence seminar, and a Workforce Advancement workshop	Low-income fathers/ father figures who are 18+ years of age with children up to 24 years	Pre-intervention outcome scores	Participants will report improved parenting behaviors 1 year after enrolling in FWP primary services	Confirmatory
R2	Primary program services which include: Nurturing Fathers parenting course, Creating a Safe Home domestic violence seminar, and a Workforce Advancement workshop	Low-income fathers/ father figures who are 18+ years of age with children up to 24 years	Pre-intervention outcome scores	Participants will report improved parenting attitudes immediately following FWP primary services	Confirmatory
R3	Primary program services which include: Nurturing Fathers parenting course, Creating a Safe Home domestic violence seminar, and a	Low-income fathers/ father figures who are 18+ years of age with children up to 24 years	Pre-intervention outcome scores	Participants will report improved co-parenting behaviors 1 year after enrolling in FWP primary services	Confirmatory

	Workforce Advancement workshop				

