4. HYPOTHESES

For each specified research question, state the hypothesized result(s) and briefly describe why these results are anticipated.

Research Question	Hypothesized Result
R1	Participants will report healthier parenting behavior one year after enrolling in the Fatherhood Works Program.
R2	Participants will report healthier parenting attitudes immediately following the Fatherhood Works Program.
R3	Participants will report healthier co-parenting behavior one year after enrolling in the Fatherhood Works Program.
R4	Participants will report healthier employment attitudes one year after enrolling in the Fatherhood Works Program.

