8. SAMPLE

8.1. TARGET POPULATION(S)

For each target population identified in Section 1.2, please describe the target population(s), and explicitly state whether the population(s) differs from those who will be broadly served by the grant. Describe how the target population will be identified. Explicitly state the unit of analysis (e.g., non-residential father, unmarried couple).

Description of Target Population	How is the population different from those who will be broadly served by the grant?	How will the target population be identified?	Unit of Analysis
Low-income fathers and father figures 18 years of age or older with children 24 years or younger in the Central Texas area	No difference, all program participants will be part of the study sample	GCT and community partners will recruit potential participants in the target population. GCT will determine eligibility as part of their intake and screening process.	Father/Father Figure

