8.2. METHODS TO PROMOTE SUFFICIENT PROGRAM PARTICIPATION

Please describe methods to promote sufficient program participation in the table below.

What methods will you use to ensure sufficient sample is recruited, enrolls, and participates in the program?	GCT and their community partners will recruit program participants, and GCT will provide incentives for workshop completion and successful program referrals. GCT has implemented organizational strategies to increase program enrollment, including prioritizing referrals to Fatherhood Works for all eligible walk-in clients. GCT also meets quarterly with its community partners to talk about progress toward meeting referral targets. The CQI process will address issues regarding program recruitment, enrollment, and completion to ensure targets are met.
--	--

Who will be responsible for recruiting the evaluation sample?	The evaluation sample will not differ from the program population, in that all participants will be invited to participate in the evaluation. Enrollment into the evaluation will be conducted by the Data Manager who will conduct the informed consent process and proctor the baseline data collection efforts.
Please describe any incentives to be offered for program participation and/or completion and/or data collection and/or participation in the evaluation.	Program Participation – GCT will provide a series of incentives for workshop completion, employment retention, and successful referrals to the program, up to \$200. Evaluation Participation – The program participation incentive for reaching 100% of primary workshop hours includes exit survey completion. No incentive will be given for entrance survey completion. A \$50 Giftogram gift card will be given to participants who complete the 1-year follow-up survey.

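### Confirmatory R2 is measured essentially in fathers still present when the program ends, but its stated population carries no such condition and the planned non-response check does not reach it

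*Protocol*

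**What the plan says.** **Collection.** Protocol 9.3 has the post-test "Collected after the completion of the primary services programming", and gives the occasion as "during the last workshop session or exit session – approximately 7 to 13 weeks after enrollment depending on delivery schedule". It is self-entered online and proctored by the Data Manager. For the 1-year survey, the same section lists an online link, "Phone interview data collection with evaluation staff", and a participant tracking team. The post-test row lists none of these.

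**Incentive.** Protocol 8.2: "The program participation incentive for reaching 100% of primary workshop hours includes exit survey completion". No separate payment for the post-test is listed.

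**Question and population.** Protocol 1.1 words R2 as "How did parenting attitude measures change from program enrollment to immediately following program completion". Protocol 1.2 classes R2 as confirmatory, gives it the same target population as R1, R3 and R4 (low-income fathers and father figures aged 18 or over), and states the expected outcome as "Participants will report improved parenting attitudes immediately following FWP primary services". The hypothesis in Protocol 4 is "Participants will report healthier parenting attitudes immediately following the Fatherhood Works Program". On how the target population differs from those served, Protocol 8.1 answers "No difference, all program participants will be part of the study sample".

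**Analysis.** SAP section 1 requires the post survey for membership of the parenting-attitude sample, does not impute missing outcomes, and applies a paired t-test to the analytic sample for each outcome. Its non-response analysis is planned for each primary outcome and sorts fathers by whether they completed the pre-survey, the follow-up survey, both or neither.

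**The concern.** A father who has stopped attending before the last or exit session has no listed way to supply a post-test, and without one he drops out of R2. Attendance to the end is unlikely to be unrelated to how a father's attitudes are developing, so those measured may differ from those enrolled. The SAP itself expects incomplete attendance, since it will report initial, halfway, 90% and 100% categories.

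R2 is one of four confirmatory questions, which Protocol 1.2 defines as those on which conclusions will be drawn. If its conclusion is read for the stated target population, it describes a wider group than the one measured. No planned analysis would show the reader how far the two groups differ.

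**Working it through.** The documents give no sample size, completion rate, post-test response rate or standard deviation for R2, and the CONSORT diagram is not in the available text. There is no stated figure to reproduce, so the check is a reading of the passages against each other, followed by an illustration on assumed values.

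**Step 1: who can have a post-test.** Protocol 9.3 ties it to the last workshop or exit session after primary services end. With no other route listed, presence at that point is in practice the condition.

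**Step 2: who enters the R2 test.** The SAP needs both the entrance and the post survey and does not impute. A father without a post-test contributes nothing.

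**Step 3: whom R2 is about.** The target population in Protocol 1.2 and the hypothesis in Protocol 4 carry no condition on reaching the end. The timing phrase in Protocol 1.1 says when attitudes are measured. No text turns it into a restriction on the population.

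**Step 4: whether the non-response analysis covers it.** It does not, for two reasons.
- It is limited to primary outcomes, and Protocol 1.1 lists R2 as secondary.
- Its categories do not use the post-test. A father with a pre-survey and a 1-year survey but no post-test is counted as a complete case, yet is absent from R2. A father with a pre-survey and a post-test but no 1-year survey is counted as pre-survey only, yet is in R2.

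**Step 5: what determines the size.** Let p be the share of enrolled fathers who reach the post-test, and let d1 and d0 be the mean change in those who do and do not reach it.

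Mean change among all enrolled = p × d1 + (1 − p) × d0

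R2 reports d1, so its error is (1 − p) × (d1 − d0). All values below are assumptions, in SD units.

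| d1 (what R2 reports) | d0 | p = 0.5 | p = 0.7 | p = 0.9 |
|---|---|---|---|---|
| 0.30 | 0.30 | 0.30 | 0.30 | 0.30 |
| 0.30 | 0.15 | 0.225 | 0.255 | 0.285 |
| 0.30 | 0 | 0.15 | 0.21 | 0.27 |
| 0.15 | 0.30 | 0.225 | 0.195 | 0.165 |

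The last three columns give the change among all enrolled. For example, at p = 0.7 with d1 = 0.30 and d0 = 0: 0.7 × 0.30 + 0.3 × 0 = 0.21, so R2 would be too high by 0.09. With the values turned round (d1 = 0.15, d0 = 0.30): 0.7 × 0.15 + 0.3 × 0.30 = 0.195, so R2 would be too low by 0.045. In the first row there is no error at any p. The documents do not say which row applies.

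**The case against.** The best reply is that R2 is worded as a question about the point of completion. Protocol 1.1 and the R2 row of Protocol 5 both place the second measurement at program completion. The SAP states openly that the post survey is required for this measure, that analytic samples will vary, and that tests apply to the analytic sample. This stands in part: the restriction can be found by a careful reader. But it is not carried into the target population, the hypothesis or the non-response plan.

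Several stronger readings are tempting, and the documents do not support them.

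- *R2 is restricted by dose received.* No minimum hours are set for the post-test. A father who missed sessions but came to the last one can be surveyed. The exit session is not defined; if it is also held for early leavers the restriction is weaker, although the opening clause of the timing rule points the other way.
- *The incentive excludes fathers below 100% of hours.* It makes the survey part of earning a payment. It is not an eligibility rule.
- *The R2 conclusion is stated for all participants.* The R2 texts say participants. The word all comes from Protocol 8.1, which concerns who enters the study, and Protocol 8.2 describes this as everyone being invited.
- *R2 overstates the change, by the reciprocal of the completion share.* That follows only if early leavers do not change at all. Motivated fathers might instead start near the top of the scale and change less.
- *R2 cannot be compared with R1, R3 and R4.* No such comparison is planned, and the questions differ in construct or time point whatever the sample.

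**Conclusion.** The point holds as a mismatch between the fathers R2 can measure and the population it names, with no planned check on the difference. It rests on reading Protocol 9.3 as the full list of post-test routes and the exit session as following completion of services.

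The consequence is that R2 **may** misstate attitude change among enrolled participants. The error is (1 − p) × (d1 − d0), and none of p, d1 or d0 is known from the documents, so neither its size nor its sign can be given. It is zero if early leavers change as much as those who stay, and small if nearly all fathers reach the post-test. This does not invalidate R2 as a description of fathers who reached the end. It should be corrected before a confirmatory conclusion is drawn for the wider target population.

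**What to change.** **While collection is open:** at the 7-to-13-week point already stated in Protocol 9.3, send the existing online post-test by link to consented fathers who missed the last or exit session. Flag these responses as unproctored. State in 9.3 what an exit session is and whether early leavers are offered one. Confirm first which platform holds the attitude items: Protocol 9.1 lists the nFORM survey, while the SAP measure table gives the OLLE post survey as the post-program source.

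**Where collection has closed** (Protocol 4 of the summary, the evaluation timeline, ends post-test collection on 5/31/2024): limit the R2 population and conclusion in Protocol 1.2, Protocol 4 (Hypotheses) and the SAP to fathers who reached the post-test.

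**In either case:**
- report the number and share of enrolled fathers contributing to R2;
- extend the SAP's non-response comparison to post-test completers versus non-completers, using the Applicant Characteristics Survey variables already named there.

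**Cost:** a link and a flag using online collection already in place, or a change of wording, plus one added comparison on data already held. The downside is some unproctored responses in R2, or a narrower R2 claim.
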